14.2 Final Analysis (End of Study)

The final analysis will be conducted after all participants have completed the study, the clinical database has been locked, the analysis populations have been approved.

The final analysis will be based on the final version of the SAP. Any deviations from the planned analysis will be documented in the CSR.

14.3 Ad-hoc Analysis (End of Study)

An ad-hoc analysis may be reran for all outputs for all patients who received Remdesivir as part of their SOC in all treatment arms.

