#### **4.4 Design Justification**

This study represents one of the first repurposed investigations of Ifenprodil in patients with COVID-19 disease. This study will provide information on the safety and clinical efficacy in the SARS-CoV-2 infected population prior to advancing to larger clinical trials, as well as provide critical information for the design of future studies in this population.

The purpose of this study is to determine whether Ifenprodil is effective and safe in the treatment of patients with COVID-19 disease. The primary measure of efficacy will be patient clinical status (on a 7-point ordinal scale) at day 15 in IP versus control group patients. This protocol is based on the recommendations of the [WHO R&D Blueprint Clinical Trials Expert Group](#).

The Phase 2b stage will be an open label study with patients, investigator, site and CRO staff aware of treatment received. The Phase 3 stage of the protocol will also include a placebo arm to allow for double-blinding.

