#### **7.4.9 Prior and Concomitant Therapies**

All medications (prescription and non-prescription), treatments, and therapies taken by the patient from screening throughout their entire participation in the study, including those initiated prior to the start of the study, must be recorded on the patient's source document and on the appropriate page of the eCRF. The dose, unit, frequency, route, indication, date the medication was started, and date the medication was stopped (if not ongoing) must be recorded.

All Investigational COVID-19 therapeutic agents used both prior to, and current to randomization and participation in the study should be captured in the CRF.

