#### **7.4.11 Prohibited Therapy**

Patient should not be taking droxidopa. Single use of ketamine is permitted. Use of unapproved/off label medications for COVID-19 treatment is permitted if they fall under the established local standard of care.

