9. PRIOR AND CONCOMITANT MEDICATIONS & THERAPIES

Prior and concomitant medications and therapies will be coded using Anatomical Therapeutic Chemical (ATC) classification system version March 2020 which is controlled by the World Health Organization Drug Dictionary (WHO-DD). Medications will be mapped to the full WHO-DD Anatomical Therapeutic Chemical (ATC) class hierarchy, with ATC Level 2, ATC Level 4 presented as the primary interest for the analysis.

Concomitant medications and therapies are additional medications or therapies taken on or after the first dose of study treatment up and including the follow up period. Medications or therapies taken before first dose of study drug and stopped before the first dose of study drug will be classified as prior medication/therapy. If missing dates prevent a clear determination as to whether the medication or therapy is concomitant, the medication will be regarded as concomitant.

The number and percentage of patients using at least one prior or concomitant medication/therapy will be displayed together with the number and percentage of patients using at least one medication/therapy within each therapeutic class and preferred term. These will be summarized under Safety population for treatment groups defined in [section 3.4](#) and repeated for concomitant medication/therapy used for different purposes: adverse events, medical history or other.

Listing of full details of prior and concomitant medications/therapy (classification, medication taken, indication (adverse events, medical history or other), corresponding AE or medical history number, dosage, unit and route, start and stop dates/ongoing status will be provided by treatment arm (grouping provided in [section 3.4](#)) sorted by patient ID and visit for the Safety population, along with the age and sex and baseline weight of the patient.

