10. TREATMENT EXPOSURE AND COMPLIANCE

SOC medications and therapies will be coded in the same manner as prior and concomitant medication/therapy with ATC Level 2, ATC Level 4 presented as the primary interest for the analysis. Summary of counts and percentages will be provided for all sites and for each site for the ITT, PPS and Safety population, with denominator being the available patients at each site.

- The Treatment Exposure (duration in days) is defined as:
Date of Last Study Drug Administration - Date of First Study Drug Administration + 1.

- The COVID-19 Treatment Exposure (duration) from randomization during the study is defined as:
Date and Last treatment - Date of Randomization + 1

- The overall COVID-19 Treatment Exposure (duration) during the study is defined as:

Date and Last treatment - Date of First COVID19 medication/treatment + 1 Both of these COVID-19 treatment exposure durations will be categorized into ≤ 15 days, > 15 days but ≤ 29 days, and > 29 days

- The Treatment Compliance is defined as:

For arm A: Total dosage taken / $(3 \times \{\text{Number of days in hospital up to 14 days}\}) \times 20$ mg=840mg)

For arm B: Total dosage taken / $(3 \times \{\text{Number of days in hospital up to 14 days}\}) \times 40$ mg=1680mg)

No treatment compliance is calculated for SOC as this differs between sites and regimen.

Treatment compliance with respect to counts and percentage of patients with $< 80\%$ and $\geq 80\%$ compliance will be reported.

- The Number of Days in Hospital (duration in days) is defined as:

Maximum of $\{\text{Date and Time of First Hospital Discharge} - \text{Date and Time of First Hospital Admission} + 1 \text{ or } 14 \text{ days}\}$.

Treatment exposure in duration and compliance will be summarized using descriptive statistics in accordance to [section 3.1](#) under ITT, PPS and Safety for treatment groups defined in [section 3.4](#). These information will be listed by Arm A and B sorted by patient ID and visit for the ITT and Safety population, along with the age, sex, baseline weight of the patient as well as the dates and times of study drug administration at each visit, whether the patient is in PPS, route and method of administration (after food, crushed) and whether drug administration was interrupted or missed and reasons for dose/study drug not administered.

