13. CHANGES TO THE PLANNED ANALYSIS

14. AN AD-HOC ANALYSIS BASED ON ALL PATIENTS WHO RECEIVED REMDESIVIR AS PART OF THEIR SOC IN ALL TREATMENT ARMS MAY BE PERFORMED AS DESCRIBED IN 14.3.

INTERIM AND FINAL ANALYSIS

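### The optional remdesivir re-run has no start-time condition, so its between-arm comparisons may not be protected by randomisation

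*SAP*

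**What the plan says.** SAP 14.3 says that an ad hoc analysis may repeat every output "for all patients who received Remdesivir as part of their SOC in all treatment arms". SAP section 13 points to that section and carries the same rule: "AN AD-HOC ANALYSIS BASED ON ALL PATIENTS WHO RECEIVED REMDESIVIR AS PART OF THEIR SOC IN ALL TREATMENT ARMS MAY BE PERFORMED AS DESCRIBED IN". Both make the analysis optional and label it ad hoc. Neither gives a start date, a baseline window or a caveat.

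Four other places bear on who would qualify:

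- Protocol 7.4.11: "Use of unapproved/off label medications for COVID-19 treatment is permitted if they fall under the established local standard of care". No limit is set on when such treatment may begin.
- Protocol 7.4.9 requires recording of all medications "taken by the patient from screening throughout their entire participation in the study, including those initiated prior to the start of the study".
- SAP section 10: "SOC medications and therapies will be coded in the same manner as prior and concomitant medication/therapy".
- SAP section 9: "Concomitant medications and therapies are additional medications or therapies taken on or after the first dose of study treatment up and including the follow up".

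On blinding, Protocol 4.4 states: "The Phase 2b stage will be an open label study with patients, investigator, site and CRO staff aware of treatment received". Randomisation is stratified by site and age only (SAP 2.6), and the primary model contains treatment, age and site (SAP 11.1).

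**The concern.** Read together, these passages let a patient enter the subset through remdesivir started after randomisation. Whoever prescribes it then can know both the arm and how the patient is doing. If either influences the decision, membership of the subset depends on arm and prognosis, and the arms within it can differ for reasons other than ifenprodil. Neither stratification nor adjustment for site and age removes such a difference.

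The re-run covers all outputs, so it includes the proportional-odds p-values for the Day 15 scale. SAP 11.1 allows p-values below 0.05 to be regarded as potentially promising for the next phase. Protocol 10.3 lists the target population and eligibility among the features to be reassessed for Phase 3. A misleading result in remdesivir-treated patients could therefore colour a design discussion, although no rule in either document ties a decision to this subset.

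**Working it through.** **The plan's own figures.** No figure is given for the remdesivir re-run. The only powered figure is the Phase 3 sample size. It reproduces, and the present point does not depend on it. With p̄ the average of the two columns of SAP Table 2:

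N = 12(1.960 + 1.282)² / [0.5596² × (1 − Σp̄³)] = 12 × 10.51 / (0.3132 × 0.874) ≈ 461, against 462 stated.

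**Illustration with no drug effect.** One input comes from the documents: 37% + 36% = 73% out of hospital at Day 15 on SOC (SAP Table 2). It is applied here to patients on remdesivir at baseline. The rest are assumptions: 30% of each arm on remdesivir before randomisation, a fraction L of an arm started later after worsening, and 30% of those late starters discharged by Day 15. The discharge proportion in the ever-treated subset is

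(0.30 × 0.73 + L × 0.30) / (0.30 + L).

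- L = 0.10: 0.249 / 0.40 = 0.6225, odds 1.649
- L = 0.15: 0.264 / 0.45 = 0.5867, odds 1.419
- L = 0.20: 0.279 / 0.50 = 0.5580, odds 1.262

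| Late starts, SOC | Late starts, active | Odds ratio for discharge, active vs SOC |
|---|---|---|
| 20% | 10% | 1.649 / 1.262 = 1.31 |
| 15% | 10% | 1.649 / 1.419 = 1.16 |
| 20% | 15% | 1.419 / 1.262 = 1.12 |
| 20% | 20% | 1.00 |
| 10% | 20% | 1.262 / 1.649 = 0.77 |

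The first row is a consistent null. If a further 10% of the active arm worsen without receiving remdesivir and also have 30% discharged, both arms have 20% worsening and can share the same overall discharge rate.

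**Check on the ordinal scale.** A simulation with no drug effect used the SOC column of Table 2. It assumed a severity signal correlated 0.5 with outcome and about half of each arm receiving remdesivir. Only the strength of the link between severity and receipt was varied (log-odds slope per SD).

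- Same slope in both arms (0, 0.5 or 1.0): common odds ratio 0.99 to 1.01. With 50 per arm, the rejection rate at two-sided 2.5% was 2.3% to 2.7% (slopes 0 and 1.0).
- SOC 0.5, active 0: odds ratio 1.22.
- SOC 1.0, active 0.5: odds ratio 1.15.
- SOC 1.0, active 0: odds ratio 1.42, rejection rate 5.8%.
- SOC 0, active 1.0: odds ratio 0.71.

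The share treated was equal in both arms throughout, so equal numbers on remdesivir do not by themselves show that the subset is comparable.

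**Size against noise.** With 50 per arm, the 20% against 10% scenario leaves 50 × 0.50 = 25 SOC patients and 50 × 0.40 = 20 in an active arm. The standard error of the log odds ratio is √(1/13.95 + 1/11.05 + 1/12.45 + 1/7.55) = 0.612. The 95% interval around 1.31 is therefore about 0.39 to 4.34. The chance of p < 0.025 is about 3.9%, against 2.5% nominal.

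**The case against.** The strongest reply is that the documents never say when remdesivir is started or that its use differs by arm. The drug is named only in SAP sections 13 and 14.3, and there only as part of standard of care. If sites give it by policy at admission, the subset is close to a baseline subgroup, and the model already adjusts for site. Late starts driven by worsening, or by a patient having no study drug, are conjecture. This stands, and it makes the point conditional: the wording leaves the timing open.

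The second reply is that little rests on the analysis. It is optional and labelled ad hoc, SAP 11.1 calls the pilot phase exploratory, and sampling error swamps the bias in the worked scenario. This also stands, and it sets the grade.

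The third is that timing can be inspected anyway, because start and stop dates are listed (SAP sections 9 and 10). This stands only in part. Listings do not stop p-values from being produced in the subset. The split between prior and concomitant use in SAP section 9 is also anchored on first dose of study drug, which SOC-only patients do not receive.

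A reader might go further and infer that the arms in the re-run are certainly no longer randomised groups, or that the rule favours ifenprodil. The documents support neither. A common prescribing rule in both arms gives no bias under the null, and unequal rules can push the estimate either way.

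**Conclusion.** The concern holds as a limited one. As worded, the subset can include patients selected after randomisation by clinicians who know the arm, so between-arm comparisons within it may not be protected by randomisation. Under the assumed rates, the discharge odds ratio with no true effect runs from 0.77 to 1.31, and is 1.00 when late starts are equal. On the ordinal scale, the simulated range was 0.71 to 1.42. All of these sizes rest on assumed prescribing patterns and say nothing about what happened in the trial. It might be inferred that the primary result is at risk because the re-run repeats the primary endpoint. It is not: the ITT analysis in SAP 11.1 does not use this subset. Severity is minor, because the analysis is optional and exploratory.

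**What to change.** In SAP 14.3 and section 13, define the subset for any between-arm comparison as patients whose remdesivir started before randomisation, using the recorded start dates (Protocol 7.4.9; SAP section 9) and randomisation dates (SAP section 5). Randomisation is the right anchor because it exists in all three arms. Tables in patients who ever received remdesivir can stay, since they describe co-exposed patients, including for safety. They should be descriptive, carry no between-arm p-values, and show the timing of remdesivir start by arm.

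The change takes a sentence or two and needs no new data. The cost is precision. If the baseline subset were half of each arm (25 per arm, an assumption), power for an odds ratio of 1.75 at two-sided 2.5% would be about 12%, against about 23% with all 50 per arm. The result should be read as an estimate with its confidence interval.

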15. SOFTWARE

- SAS[®] Version 9.4 or higher (SAS Institute, Cary, North Carolina, USA).

16. TABLES, LISTINGS AND FIGURES

Please refer to mock shell template. A separate DSMB tables listings and figures mock shell is also available.

